#### **3.6.3 Off Protocol Therapy and Off Study Procedure**

Authorized staff must notify Central Registration Office (CRO) when a subject is taken off protocol therapy and when a subject is taken off-study. A Participant Status Update Form from the web site (<http://home.ccr.cancer.gov/intra/eligibility/welcome.htm>) main page must be completed and sent via encrypted email to: NCI Central Registration Office [[contact]](mailto:[contact]).

## **4 CONCOMITANT MEDICATIONS/MEASURES**

### **4.1 HEMATOLOGIC AND BLOOD PRODUCT SUPPORT**

Blood product support should be provided to maintain platelets > 20,000 cells/mcl, Hgb > 8.0 gm/dl and as clinically indicated. Growth factor support is not permitted with exception of administration of filgrastim. Filgrastim will not be administered prophylactically but may be administered during cycle 1 if a patient experiences neutropenic sepsis, or during subsequent cycles if clinically indicated.

### **4.2 ANTIEMETIC THERAPY AND TRANSAMINITIS PROPHYLAXIS**

Ondansetron (or other drugs from this same class of anti-emetics, as per investigator preference) prior to and after mithramycin as needed. Additional antiemetic therapy may be provided by either intravenous or oral route as needed. Patients that experience significant nausea during cycle one may be offered aprepitant for subsequent cycles. Patients will receive either dexamethasone 8 mg

PO or dexamethasone 12mg IV the evening prior to the first dose of mithramycin and then will receive dexamethasone 12 mg IV daily through at least the first course of therapy.

### **4.3 ANTI-DIARRHEAL**

Antidiarrheal agents will be prescribed using standard clinical practice guidelines at the preference of the investigator.

### **4.4 ELECTROLYTE REPLACEMENT**

Electrolyte replacement will be provided to maintain serum levels within normal limits.

## **5 CORRELATIVE STUDIES / BIOSPECIMEN COLLECTION**

### **5.1 PHARMACOKINETIC (PK) SAMPLING**

Detailed plasma pharmacokinetic (PK) sampling of mithramycin will be performed prior to and at the completion of the first dose of mithramycin during cycle 1 and cycle 2 of course 1 (up to 11 tubes, Refer to details in [Appendix 3](#)). In addition, through and end of infusion samples will be obtained with the day 2, 4 and 7 doses to assess mithramycin accumulation, and samples will be obtained 24 and 48 hours after the day 7 dose of mithramycin on days 8 and 9, respectively. PK analysis will be performed at the NCI, Genitourinary Malignancies Branch (GMB). Samples will be stored in the TEL and batched and later transferred to the [name] Lab on dry ice for analysis. Please refer to section [5.3.2](#) for instructions on sample processing.

### **5.2 STUDIES ON TUMOR TISSUE**

Tissue biopsies will be obtained by minimally invasive methods such as CT guided percutaneous, endoscopic, laparoscopic or video-assisted thoracoscopic techniques at baseline and on day 8 ( $\pm 2$  days) of the second cycle. If insufficient tissue was obtained or if there was harm related to the first biopsy, a second biopsy will not be obtained. Should a patient experience a dramatic clinical response to treatment, additional tumor tissue biopsies may be requested, but are not required. At the time of tissue acquisition, immediate on-site cytopathologic analysis will be performed to confirm that malignant cells are present in the biopsies, to enhance potential yield and improve subsequent evaluation of molecular endpoints. Samples will be placed in saline in an orange top tube on wet ice and transported to the Thoracic Epigenetics Lab for further processing. In the Thoracic Epigenetics Lab, a portion will be separated and frozen on dry ice for RNA collection for microarray and/or gene signature evaluation, using a customized panel of < 100 genes, microRNA and DNA methylation sites noted to be modulated in human cancer xenografts in mice treated intraperitoneally with mithramycin. If sufficient tissue is available, another portion will be imbedded in paraffin for subsequent immunostaining experiments, focusing on expression of genes correlating with treatment response in our preclinical experiments. Additional tissue will be used to establish cell lines to examine effects of mithramycin on the epigenome and stem cell signaling *in vitro*, in an attempt to correlate these findings with results obtained from analysis of tumor biopsies, or to examine SP. All of the analyses, which are predicated on acquisition of sufficient biopsy materials, will be performed in the Thoracic Epigenetics Lab/TGIB under direction of the PI.

*Note:* The patient will consent to the optional biopsy at the time of the procedure. If the patient refuses the optional biopsy at that time, the refusal will be documented in the medical record and in the research record.

### **5.3 SAMPLE STORAGE, TRACKING AND DISPOSITION**

#### **5.3.1 Thoracic Epigenetics Section, TOSB/NCI**

This study will be conducted within the Thoracic Epigenetics Section, TGIB/NCI. Sample collection and initial processing will be performed in the Thoracic Epigenetics Laboratory. Samples will be stored in designated monitored freezers (at least -20°C). All samples obtained on this study will be tracked using LabMatrix. Pharmacokinetic samples will be analyzed at the NCI PETS. Samples will be identified and tracked using unique identifiers linked to each subject's unique patient number (study number). Codes linking personal identifiable information to the unique identifier will be stored in secure, computer servers with limited coded access or locked file cabinets in Thoracic Epigenetics Section, TOSB/NCI with access limited to the PI or study coordinator. Focused gene expression, microRNA, and DNA methylation analysis will be performed by nano-string and pyrosequencing techniques in [name] laboratory. The study will remain open and status reported to the NCI IRB until all samples have been analyzed, reported or destroyed. Unintentional loss or destruction of any samples will be reported to the NCI IRB as part of annual continuing reviews. Any use of samples not outlined in Section 5 will require prospective NCI IRB review and approval.

At the conclusion of this study, those samples from patients who have not authorized the continued use of their specimens for research purposes will be destroyed in accordance with the environmental protection laws, regulations and guidelines of the Federal Government and the State of Maryland. Any unintentional destruction or loss of the specimens will be reported to the IRB. Patients who agree to allow continued use of their specimens for research purposes will be enrolled on 06-C-0014.

##### **Sample Data Collection**

All samples sent to the Blood Processing Core (BPC) will be barcoded, with data entered and stored in the LABrador (aka LabSamples) utilized by the BPC. This is a secure program, with access to LABrador limited to defined [name] lab personnel, who are issued individual user accounts. Installation of LABrador is limited to computers specified by [name]. These computers all have a password restricted login screen. All [name] lab personnel with access to patient information annually complete the NIH online Protection of Human Subjects course.

LABrador creates a unique barcode ID for every sample and sample box, which cannot be traced back to patients without LABrador access. The data recorded for each sample includes the patient

ID, name, trial name/protocol number, time drawn, cycle time point, dose, material type, as well as box and freezer location. Patient demographics associated with the clinical center patient number are provided in the system. For each sample, there are notes associated with the processing method (delay in sample processing, storage conditions on the ward, etc.).

Sample bar-codes are linked to patient demographics and limited clinical information. This information will only be provided to investigators listed on this protocol, via registered use of the LABrador. It is critical that the sample remains linked to patient information such as race, age, dates of diagnosis and death, and histological information about the tumor, in order to correlate genotype with these variables

### **Sample Storage and Destruction**

Barcoded samples are stored in barcoded boxes in a locked freezer at either -20 or -80°C according to stability requirements. These freezers are located onsite in the BPC and offsite at NCI Frederick Central Repository Services in Frederick, MD. Visitors to the laboratory are required to be accompanied by laboratory staff at all times.

Access to stored clinical samples is restricted. Samples will be stored until requested by a researcher named on the protocol. All requests are monitored and tracked in LABrador. All researchers are required to sign a form stating that the samples are only to be used for research purposes associated with this trial (as per the IRB approved protocol) and that any unused samples must be returned to the BPC. It is the responsibility of the NCI Principal Investigator to ensure that the samples requested are being used in a manner consistent with IRB approval.

Following completion of this study, samples will remain in storage as detailed above. Access to these samples will only be granted following IRB approval of an additional protocol, granting the rights to use the material.

If, at any time, a patient withdraws from the study and does not wish for their existing samples to be utilized, the individual must provide a written request. Following receipt of this request, the samples will be destroyed (or returned to the patient, if so requested), and reported as such to the IRB. Any samples lost (in transit or by a researcher) or destroyed due to unknown sample integrity (i.e. broken freezer allows for extensive sample thawing, etc.) will be reported as such to the IRB.

## **6 DATA COLLECTION AND EVALUATION**

### **6.1 DATA COLLECTION**

The Principal Investigator will be responsible for the collection, maintenance, and quality control of the study data. All clinical data collected for each study subject will be entered into the C3D database. Pharmacokinetic and pharmacodynamic research specimens will be entered into Labmatrix. The Principal Investigator is responsible for maintaining any source documentation related to the study, including any films, tracings, computer discs or tapes. The principal investigator, associate investigators/research nurses and/or a contracted data manager will assist with the data management efforts. All data obtained during the conduct of the protocol will be kept in secure network drives or in approved alternative sites that comply with NIH security standards. Primary and final analyzed data will have identifiers so that research data can be attributed to an individual human subject participant. The Sponsor and its monitoring agency will have access to C3D and Labmatrix for data monitoring and verification. The investigators will allow study monitors and/or the Food and Drug Administration (FDA) to inspect study documents (e.g. consent

forms, drug distribution forms, IRB approval) and pertinent hospital or clinical records for confirmation of data throughout the study period.

**End of study procedures:** Data will be stored according to HHS, FDA regulations, and NIH Intramural Records Retention Schedule as applicable.

**Loss or destruction of data:** Should we become aware that a major breach in our plan to protect subject confidentiality and trial data has occurred, the IRB will be notified.

### **6.1.1 Source Documents**

Source documents are original documents, data and records which include hospital records, clinic and office charts, laboratory data/information, patient diaries or evaluation checklists, pharmacy dispensing and other records, recorded data from automated instruments, microfiches, photographic negatives, microfilm or magnetic media, x-rays. The Principal Investigator will permit trial-related monitoring, audits, IRB review, and regulatory inspections, providing direct access to source data documents.

## **6.2 ROUTINE DATA COLLECTION**

Following registration, all adverse events will be described in the source documents, reviewed by the designated research nurse, and captured in C3D.

- During the follow up period (more than 30 days following the last treatment), only those events that are serious, unexpected, and related to the treatment will be captured in C3D.
- All toxicities occurring within 30 days of treatment will be followed until resolution or return to baseline.

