In general, the most frequent toxicities observed were nausea, vomiting, elevated liver function tests, infusional fever, mucositis, bleeding tendencies, thrombocytopenia, electrolyte abnormalities, proteinuria and elevated BUN/creatinine (summarized in ). Unfortunately, there was no systematic investigation of these toxicities, and it is unclear what levels of supportive care these patients received. For example, nausea and vomiting occurred quite frequently; however, in at least two reports, nausea was controlled with phenothiazines or other anti-emetics .

Hemorrhage was the most profound toxicity observed in patients receiving mithramycin. In early reports hemorrhage was attributed to thrombocytopenia, and accounted for 3 deaths in 84 patients . Subsequent studies revealed that bleeding was dose-related, occurring in 5.4% of 1150 patients treated at 30 mcg/kg/day or more . Bleeding tended to occur around day 4 of treatment, which is atypical of chemotherapy-induced thrombocytopenia. In addition, it appears that platelet counts remained >20,000/mcL in most of the patients experiencing hemorrhage, suggesting that bleeding was due to underlying clotting factor deficiencies or dysregulation of coagulation pathways. In all the cases of hemorrhage reported in the literature, it is not clear if the patients were taking any anti-coagulation medications, what type of blood product support was provided, how effective the blood product support was in that era, or what specific clinical and laboratory abnormalities were seen prior to the hemorrhage. Therefore, the frequency and severity of hemorrhage from mithramycin administered in the current era are unknown. Nevertheless, hemorrhage must be considered a rare, but serious potential toxicity of mithramycin therapy.

Additional rare but significant side effects attributable mithramycin include toxic epidermal necrolysis , and possible potentiation of anthracycline-mediated cardiotoxicity . The true incidences of these toxicities are unknown and are not discussed in the package insert from Pfizer, or the previously filed IND for mithramycin.

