#### **7.1.3 Unexpected adverse reaction**

An adverse event or suspected adverse reaction is considered "unexpected" if it is not listed in the investigator brochure or is not listed at the specificity or severity that has been observed; or, if an investigator brochure is not required or available, is not consistent with the risk information described in the general investigational plan or elsewhere in the current application. "Unexpected" also refers to adverse events or suspected adverse reactions that are mentioned in the investigator brochure as occurring with a class of drugs or as anticipated from the pharmacological properties of the drug, but are not specifically mentioned as occurring with the particular drug under investigation.

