#### **7.2.2 NCI-IRB Requirements for PI Reporting Continuing Review**

The protocol PI will report to the NCI-IRB:

1. A summary of all protocol deviations in a tabular format to include the date the deviation occurred, a brief description of the deviation and any corrective action.
2. A summary of any instances of non-compliance
3. A tabular summary of the following adverse events:
  - All Grade 2 **unexpected** events that are possibly, probably or definitely related to the research;
  - All Grade 3 and 4 events that are possibly, probably or definitely related to the research;
  - All Grade 5 events regardless of attribution;
  - All Serious Events regardless of attribution.

**NOTE:** Grade 1 events are not required to be reported.

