## **7.3 IND SPONSOR REPORTING CRITERIA**

### **7.3.1 Expedited Adverse Event Reporting Criteria to the IND Sponsor**

During the first 30 days after the subject receives investigational agent/intervention, the investigator must immediately report to the sponsor, using the mandatory MedWatch form 3500a or equivalent, any serious adverse event, whether or not considered drug related, including those listed in the protocol or investigator brochure and must include an assessment of whether there is a reasonable possibility that the drug caused the event. For serious adverse events that occur more than 30 days after the last administration of investigational agent/intervention, only report those that have an attribution of at least possibly related to the agent/intervention.

Required timing for reporting per the above guideline:

- Deaths (except death due to progressive disease) must be reported via email within 24 hours. A complete report must be submitted within one business day.
- Other serious adverse events as well as deaths due to progressive disease must be reported within one business day

Events will be submitted to the Center for Cancer Research (CCR) at: [[contact]](mailto:[contact]) and to the CCR PI and study coordinator.

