## **8 STATISTICAL CONSIDERATIONS**

Prior to amendment F, the protocol enrolled 12 evaluable patients, and there were no clinical responses, but dose-limiting hepatotoxicity associated with ABCB4 and ABCB11 genotypes was identified. Thus, the results from these initial 12 patients will be reported as a separate group, and accrual will begin again using the same phase II design as initially proposed, but restricted to patients with favorable SNPs, and receiving the modified dose regimen described in amendment F. Thus, beginning with amendment F, the primary endpoint of this study will be objective response by RECIST criteria v 1.1. Patients will be analyzed in two cohorts (primary thoracic malignancy; extra-thoracic malignancy metastatic to the chest). The best response to mithramycin will be examined for each cohort. In each cohort, the trial will seek to rule out an unacceptably low 5% objective response rate (ORR;  $p_0=0.05$ ), in favor of a higher response rate of 30% ( $p_1=0.30$ ). With  $\alpha=0.10$  (probability of accepting a poor treatment=0.10) and  $\beta = 0.10$  (probability of rejecting a good treatment=0.10), the study will initially enroll 7 evaluable patients in each stratum, and if 0 of the 7 have a response, then no further patients will be accrued in that cohort. If 1 or more the first 7 in a cohort have a response, then accrual would continue until a total of 21 evaluable patients have enrolled in that cohort. As it may take several weeks to determine if a patient has experienced a response, a temporary pause in the accrual to the trial may be necessary to ensure that enrollment to the second stage is warranted. If there are 1 to 2 responses in 21 patients, this would be an uninterestingly low response rate, while if there were 3 or more responses in 21 patients, then this would be sufficiently interesting to warrant further study of the patients from that cohort in later trials. Under the null hypothesis (5% response rate), the probability of early termination in each cohort is 70%.

With two cohorts, up to 42 evaluable patients may be required to be accrued, in addition to the 12 enrolled prior to amendment F. It is expected that 10-15 patients per year may enroll onto this study. Thus, 3-4 years additional may be needed to enroll 42 additional evaluable patients. To allow for a small number of inevaluable patients, and to account for the 12 enrolled prior to amendment F, the accrual ceiling will be set at 57.

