## 8.1 METHODS OF ANALYSIS

Patients who are considered evaluable for response will be included in an analysis of time to progression. Time to progression will be estimated using the product-limit method of Kaplan and Meier. The probability of progression free survival at 6 months will be summarized. Response rates will be calculated as the percent of patients whose best response is a CR or PR, and the fraction of responses obtained will have a 95% confidence interval, which takes into consideration the two-stage nature of the design. Toxicity information recorded will include the type, severity, time of onset, time of resolution, and the probable association with the study regimen. Tables will be constructed to summarize the observed incidence by severity and type of toxicity.

**Time to progression** will be taken as the number of days from enrollment until: (1) disease progression; (2) death because of treatment complications; (3) resection of measurable tumor; or (4) last patient follow-up whichever is first. Patients will be considered to have experienced a progression event if (1) or (2) occurs. Otherwise, the patient will be considered censored for time to progression.

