##### Less frequent

- Drowsiness
- Fever
- Headache
- Mental depression
- Pain, redness, soreness, or swelling at injection site
- Unusual tiredness or weakness

- f) Gastrointestinal bleeding (bloody or black, tarry stools; vomiting of blood)
- g) hepatotoxicity (yellow eyes or skin)
- h) Epistaxis, hematemesis
- i) Leukopenia (sore throat and fever)—incidence about 6%
- j) Petechial bleeding
- k) Thrombocytopenia
- l) Toxic epidermal necrolysis (flushing or redness or swelling of face; skin rash)—possible early symptoms of overdose

Note: Hemorrhagic diathesis—Incidence more frequent with doses of more than 30 mcg (0.03 mg) per kg of body weight a day and/or for more than 10 doses.

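### After 30 days, section 6.2 keeps a serious related event in the trial database only if it is unexpected, a narrower rule than sponsor reporting in section 7.3.1

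*Combined protocol and SAP*

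**What the plan says.** Section 6.2 sets the rule for what enters C3D. Once a patient is more than 30 days past the last treatment, "only those events that are serious, unexpected, and related to the treatment will be captured in C3D". The same section says that toxicities occurring within 30 days of treatment are followed until they resolve or return to baseline.

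Section 7.3.1 covers the same late period for reporting to the IND sponsor. For serious adverse events the instruction is to "only report those that have an attribution of at least possibly related to the agent/intervention". It sets no test of expectedness.

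Section 7.2.2, on continuing review by the IRB, asks for a table that includes "All Serious Events regardless of attribution", again with no test of expectedness for serious events.

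Section 7.1.3 defines an event as unexpected "if it is not listed in the investigator brochure or is not listed at the specificity or severity that has been observed". If there is no brochure, it refers to the risk information in the investigational plan or the current application.

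Section 6.1 makes C3D the database for all clinical data collected on each subject. Section 8.1 plans the safety summary: "Tables will be constructed to summarize the observed incidence by severity and type of toxicity".

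**The concern.** Toxicity is a secondary objective (section 1.1.2). A rule that limits late capture to serious, related events would be an ordinary reporting window. Adding expectedness makes the rule select on how familiar the harm is: an unfamiliar late event is kept, while one the protocol already names is dropped.

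The protocol gives reasons to want the known harms counted. Section 1.3.3 says that "hemorrhage must be considered a rare, but serious potential toxicity of mithramycin therapy" and that its frequency and severity under present-day care are not known. Section 8 records that in the 12 patients treated before amendment F "dose-limiting hepatotoxicity associated with ABCB4 and ABCB11 genotypes was identified". If a late event of a known type is written up for the sponsor but has no C3D record, incidence tables drawn from C3D would not show it, and the database and the safety file would differ for a reason that the 8.1 tables would not reveal.

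**Working it through.** The plan gives no figure to reproduce and no arithmetic applies. The check is to set the rules side by side for an event that starts more than 30 days after the last treatment.

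| Late event | C3D (6.2) | Sponsor (7.3.1) | IRB table (7.2.2) |
|---|---|---|---|
| Serious, related, unexpected | Yes | Yes | Yes |
| Serious, related, expected | No | Yes | Yes |
| Serious, only possibly related, unexpected | Depends on how *related* is read | Yes | Yes |
| Serious, unrelated | No | No | Yes |

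1. **The gap.** The second row differs between 6.2 and 7.3.1, and the only cause is the word *unexpected* in 6.2. The third row shows a smaller mismatch: 6.2 does not say what degree of attribution counts as related, whereas 7.3.1 does.

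2. **What can fall in it.** Under 7.1.3 an event is expected when it is listed at the specificity and severity observed. Section 11.1.2 lists hepatotoxicity, gastrointestinal bleeding, petechial bleeding and thrombocytopenia. Section 1.3.3 describes fatal hemorrhage, and section 8 describes dose-limiting hepatotoxicity. A late event matching such a description would be expected, and 6.2 would exclude it.

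3. **Bleeding.** Section 6.3.1 keeps grade 1 events out of C3D but excepts bleeding, which is to be captured whatever its grade. Read narrowly, the exception lifts only the grade 1 exclusion, and the late filter in 6.2 still applies. Read broadly, it captures all bleeding at any time and contradicts 6.2. The text does not decide between these readings. No such exception exists for hepatotoxicity, so that is where the gap is clearest.

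4. **Link to the tables.** Section 8.1 refers to toxicity information that is recorded, without naming its source. Section 6.1 makes C3D the clinical database, and the documents name no other source for the tables. That the tables would come from C3D is a reasonable inference, not a stated fact.

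5. **Who is in the late window.** Under section 3.5.4, patients with stable or responding disease are seen every 2 months until they meet off-study criteria. Under section 3.6.2, progression takes a patient off study unless a related serious event is being followed. The window exists, but mainly for patients without progression.

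**The case against.** The strongest reply is that almost nothing will fall in the gap. Section 1.3.3 puts bleeding at around day 4 of treatment. In section 1.3.4, eight of the 12 patients had dose-limiting transaminitis, which was transient, without symptoms and always seen on day 4, and none of the 12 bled. Section 1.3.2.1 gives a mean elimination half-life of 10.6 hours from three patients; 30 days is 720 hours, and 720 / 10.6 is about 68 half-lives. Toxicities that begin within 30 days are followed to resolution. This stands, and it is the main reason to rate the point minor. It makes late first onset unlikely without making the rule consistent.

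A second reply is that expectedness is not settled. The investigator brochure is not among the documents, and section 11.1.2 lists effects without grades. A serious hepatic event more than a month after dosing could be judged outside the listed severity and so be captured. This also stands. The gap covers only events at a listed specificity and severity, and expectedness is inferred here from the protocol's own risk text.

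A third reply is that nothing is lost: section 6.2 requires adverse events to be described in source documents, and the sponsor and IRB receive the serious ones. That is correct for oversight. It does not put the event into the trial's toxicity tables, because no section says that expedited reports feed them.

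A reader might go further and infer that late hemorrhage is definitely excluded from the database. The bleeding exception in 6.3.1 prevents that conclusion; the most that can be said is that the sections do not agree.

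**Conclusion.** The mismatch between 6.2 and 7.3.1 is real and lies in the stated rules. Followed as written, 6.2 leaves out of C3D a late, serious, related event at a listed specificity and severity that 7.3.1 sends to the sponsor. Hepatotoxicity is the clear case; late bleeding is ambiguous.

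The size cannot be estimated from the documents, and the timing evidence suggests very few events. Any omission would run in one direction, against known harms, and would lower the tabulated incidence only if the affected patient had no earlier captured event of the same type. The primary endpoint and the two-stage stopping rule are not affected.

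Two stronger readings are tempting. One is that the toxicity results are materially biased downward; the documents give no late-event rate to support that. The other is that the database could never be reconciled with the safety file; source documents, sponsor reports and the monitoring in section 7.4.2 would allow each difference to be traced.

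The conclusion rests on two assumptions: that the 8.1 tables are built from C3D, and that the brochure's listing resembles the protocol's risk text. Severity: minor.

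**What to change.** - In section 6.2, delete *unexpected* and replace *related* with *at least possibly related*, so that late capture in C3D matches section 7.3.1.
- In section 6.3.1, state how the bleeding exception applies more than 30 days after the last treatment, consistently with the revised 6.2.
- In section 8.1, state that the toxicity tables include these late records.

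The cost is a short wording change and a few extra database entries for events already being written up for the sponsor. No additional visits, tests or patients are needed.
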